### **13.7 Publications and Clinical Study Report**

### **13.7.2 Clinical Study Report**

A clinical study report, written in accordance with the current ICH E3 Guideline, will be submitted in accordance with local regulations.

1

**3 MODIFICATIONS**

## **4 INTRODUCTION**

Study VX20-445-121 (Study 445-121) is a Phase 3b open-label study evaluating the safety of elexacaftor (ELX, VX-445) in triple combination (TC) with tezacaftor (TEZ) and ivacaftor (IVA) in subjects with cystic fibrosis (CF) who complete a parent study (VX19-445-117 or VX20-445-126).

This statistical analysis plan (SAP) is based on the most recent approved clinical study protocol (CSP), the most recent approved electronic case report form (eCRF), and the most recent approved eCRF completion guidelines.

This SAP (Methods) documents the planned statistical analyses of safety endpoints defined in the VX20-445-121 study protocol. It also documents analyses for additional safety variables not specified in the protocol, which will provide supportive information for the scientific understanding of the drug entity.

The Vertex Biometrics Department will perform the statistical analysis of safety data; SAS (Version 9.4 or higher) will be used to generate all statistical outputs (tables, figures, listings, and datasets). The SAP will be finalized and approved prior to the clinical database lock. Any revisions to the approved SAP will be documented and approved in an amendment to the SAP.

## **5 STUDY OBJECTIVES**

### **5.1 Primary Objective**

To evaluate the safety and tolerability of ELX/TEZ/IVA in subjects with CF.

## **6 STUDY ENDPOINTS**

### **6.1 Primary endpoint**

Safety and tolerability of treatment with ELX/TEZ/IVA based on adverse events (AEs), clinical laboratory values, ECGs, vital signs, and pulse oximetry.

## **7 STUDY DESIGN**

### **7.1 Overall Design**

[figure not shown]
This is a Phase 3b, multicenter, open-label study for subjects who complete a parent study (VX19-445-117 or VX20-445-126) and meet eligibility criteria (Section 8 of the CSP). Subjects will receive a dose of ELX 200 mg once daily (qd)/TEZ 100 mg qd/IVA 150 mg every 12 hours (q12h). A schematic of the study design is shown in Figure 7-1.

For treatment continuity in regions where ELX/TEZ/IVA is not commercially available, an option to return to this study will be offered to subjects who depart this study to enroll in another qualified Vertex study based on the following:

- Subjects have received open-label ELX/TEZ/IVA during the other study's Run-in Period but have not received study drug in the Treatment Period of the other study, and
- Meet all eligibility criteria for this study (Section 8 of the CSP) at their Returning Visit.

Subjects who resume participation in this study will resume treatment with study drug after completion of a Returning Visit. Resumption of participation in this study following departure to another qualified Vertex study will be permitted only once.

**Figure 7-1 VX20-445-121 Study Design**

ELX: elexacaftor; IVA: ivacaftor; TEZ: tezacaftor

Note: Figure is not drawn to scale.

## 7.2 Sample Size and Power

The primary objective of the study is the evaluation of the safety of ELX/TEZ/IVA. This is an open-label extension study that will enroll the subjects from parent studies who meet eligibility criteria in this study.

Up to approximately 160 subjects are expected to enroll in this open-label extension study.

## 8 ANALYSIS SETS

The **All Subjects Set** is defined as all subjects who were enrolled (defined as subject having data in the clinical database) in this study. This analysis set will be used for individual subject data listings and the disposition summary table, unless otherwise specified.

The **Safety Set** is defined as all subjects who have received at least 1 dose of study drug in this study. This analysis set will be used for subject demographics and baseline characteristics and for all safety analyses unless otherwise specified.

## 9 STATISTICAL ANALYSIS

### 9.1 General Considerations

The precision standards for reporting safety variables are provided in an internal Biometrics document that specifies the programming rules including the precision for derived variables.

**Continuous variables** will be summarized using the following descriptive summary statistics: the number of subjects (n), mean, SD, median, minimum value (min), and maximum value (max).

**Categorical variables** will be summarized using counts and percentages.

**Baseline value**, unless otherwise specified, will be the most recent non-missing measurement (scheduled or unscheduled) collected before the first dose of ELX/TEZ/IVA in a parent study, as applicable.

**Change (absolute change) from baseline** will be calculated as Post-baseline value – Baseline value.

**Treatment-emergent (TE) Period** will include the time period starting from the date of the first dose of study drug of this open-label study to 28 days after the last dose of the study drug, or to the completion date of study participation (as defined in Section 9.1.5 of study protocol), whichever occurs first.

**Unscheduled visits:** Unscheduled visit measurements will be included in analysis as follows:

- 1) In scheduled visit windows per specified visit windowing rules
- 2) In the derivation of baseline and last on-treatment measurements
- 3) In the derivation of maximum and minimum values during the TE period
- 4) In individual subject data listings as appropriate

**Visit windowing rules:** The analysis visit windows for protocol-defined visits are provided in [Appendix A](#).

**Incomplete/missing data** will not be imputed, unless specified otherwise.

**Outliers:** No formal statistical analyses will be performed to detect or remedy the presence of statistical outliers, unless specified otherwise.

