### **3 SCHEDULE OF ASSESSMENTS**

Schedules of assessments is in Table 3-1. All visits will be scheduled relative to the Day 1 Visit in this study.

Assessments may be performed in any order when more than 1 assessment is required at a particular time point, unless noted otherwise. All assessments should be performed before study drug dosing (Section 9.6), unless noted otherwise.

Subjects who depart this study to enroll in another qualified Vertex study, and who meet the eligibility criteria in Section 8, may resume participation in this study only once.

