### **12.3           Statistical Analysis**

#### **12.3.1        General Considerations**

All individual subject data for subjects who were enrolled or received at least 1 dose of study drug will be presented in individual subject data listings.

**Continuous variables** will be summarized using the following descriptive summary statistics: the number of subjects (n), mean, SD, median, minimum value (min), and maximum value (max).

**Categorical variables** will be summarized using counts and percentages.

**Baseline value**, unless specified otherwise, will be defined as the most recent non-missing measurement (scheduled or unscheduled) collected before the first dose of ELX/TEZ/IVA either in a parent study or this study, as applicable. For assessments collected in duplicate or triplicate, the baseline value will be defined as the average of non-missing values.

**Change (absolute change) from baseline** will be calculated as Post-baseline value – Baseline value.

**TE Period** will include the time from the first dose of study drug in this study to 28 days after the last dose of study drug or to the completion of study participation (as defined in Section 9.1.5), whichever occurs first. For subjects who enroll in another qualified Vertex study before completing this study and resume participation in this study, the TE Period will exclude the time spent in the other study.

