### **9.3.3        *Electrocardiogram***

For the following ECG interval measurements during the TE period, a summary of observed values and change from baseline values will be provided at each visit (in msec): RR, PR, QT, and QT corrected for HR (QTcF), QRS duration, and HR (beats per minute).

The number and percentage of subjects meeting at least 1 threshold analysis criterion event during the TE period will be summarized. The threshold analysis criteria are provided in [Appendix E](#).

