### **9.3.5        *Pulse Oximetry***

For the percent of oxygen saturation measurements using pulse oximetry during the TE period, a summary of observed values and change from baseline values will be provided at each visit.

The number and percentage of subjects with shift changes from baseline (normal/missing and low according to the reference range) to the lowest percent of oxygen saturation during the TE period will be summarized.

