## 12 APPENDICES

### Appendix A: Analysis Visit Windows for Safety Assessments

Table 12-1 Analysis Visit Windows Safety Assessments			
Assessment	Visit	Target Study Day	Analysis Visit Window (in study days)
Weight, Height and BMI	Baseline	--	defined in section 9.1
	OL Week 12	85	[1, 127] where Day 1 is post-dose measurement
	OL Week 24	169	(127, 211]
	OL Week 36	253	(211, 295]
	OL Week 48	337	(295, 351]
	OL Safety Follow-up	Not applicable	Use nominal visit
Vital Signs Hematology Serum Chemistry	Baseline	--	defined in section 9.1
	OL Week 12	85	[1, 127] where Day 1 is post-dose measurement
	OL Week 24	169	(127, 211]
	OL Week 36	253	(211, 295]
	OL Week 48	337	(295, 351]
	OL Safety Follow-up	Not applicable	Use nominal visit
Standard 12-lead ECG	Baseline	--	defined in section 9.1
	OL ETT or Departing	Not applicable	Use nominal visit (ETT or Departing Visit)
	OL Safety Follow-up	Not applicable	Use nominal visit
Coagulation 	Baseline	--	defined in section 9.1
	OL Week 24	169	[1, 253] where Day 1 is post-dose measurement
	OL Week 48	337	(253, 351]
	OL Safety Follow-up	Not applicable	Use nominal visit

Notes:

 Visit name for analysis purpose is used to report data in tables and figures.

 The analysis visit windows will be applied using the following rules for both scheduled and unscheduled visits:

1. If no numerical measurement is available within a visit window, the measurement will be considered missing for the visit.
2. If there is more than 1 numerical measurement available within a visit window, use the following rules:
  - i. The measurement closest to the target day will be used; or
  - ii. If there are multiple measurements with the same distance from the target day, the latest measurement will be used. If the latest measurement cannot be determined, then unscheduled visit will be selected.

 For measurement collected on the date of first dose of study drug in Treatment Period, if it cannot be determined whether the measurement is before or after the first dose:

1. Scheduled measurement will be treated as pre-dose observation.
2. Unscheduled measurement will be treated as post-dose observation.

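### The SAP starts the TE Period on the first-dose date and does not carry its pre-dose rule into the threshold and lowest-SpO2 analyses, so pre-dose Day 1 values can be counted there

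*SAP*

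**What the plan says.** **Start of the TE Period.** In SAP 9.1 the period "will include the time period starting from the date of the first dose of study drug of this open-label study". In protocol 12.3.1 it "will include the time from the first dose of study drug in this study to 28 days after the last dose of study drug". The two definitions end the period in the same way.

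**Timing of Day 1 assessments.** Protocol Section 3: "All assessments should be performed before study drug dosing (Section 9.6), unless noted otherwise". Protocol 11.2.2 repeats this for Day 1 blood samples and 11.2.5 for pulse oximetry. Under protocol 9.1.1 the first dose is normally given on Day 1.

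**Analyses tied to the TE Period.** SAP 9.3.3 says of ECGs: "The number and percentage of subjects meeting at least 1 threshold analysis criterion event during the TE period will be summarized". SAP 9.3.2 (laboratory) and 9.3.4 (vital signs) carry the same sentence. SAP 9.3.5 tabulates the SpO2 shift from baseline "to the lowest percent of oxygen saturation during the TE period will be summarized". SAP 9.1 also lists, among the uses of unscheduled values: "In the derivation of maximum and minimum values during the TE period".

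**Pre-dose rules.** These are in SAP Appendix A. In Table 12-1 the first window for weight, vital signs, hematology and chemistry reads, after its opening bracket, "1, 127] where Day 1 is post-dose measurement". Coagulation has the same restriction on a longer window. Note 3 applies when it is unclear whether a first-dose-date measurement came before or after the dose: "Scheduled measurement will be treated as pre-dose observation". An unscheduled one is taken as post-dose. The ECG derivation in the same appendix uses every ECG value in the TE Period for threshold purposes.

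**The concern.** All four data types are components of the primary endpoint. A period that opens on a calendar date includes everything measured on that date, whether before or after the tablets were taken. A threshold table built on that period could therefore report as treatment-emergent an abnormality that was present before any dose in this study.

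The usual safeguard does not help. In many trials the pre-dose Day 1 value is the baseline, so restricting to post-baseline data removes it. Here SAP 9.1 takes baseline before the first ELX/TEZ/IVA dose in a parent study. For a subject with such a baseline, the Day 1 value of this study is itself post-baseline, and a program that follows the text has no reason to drop it.

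The point is separate from the choice of baseline, because it also affects criteria that use no baseline, such as an absolute QTc limit.

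**Working it through.** There is no figure in the plan to reproduce. The planned number, up to about 160, is expected roll-over enrolment with no formula, and SAP 9.3 is descriptive only. The check is mainly one of text.

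**Step 1. Is a pre-dose Day 1 value inside the TE Period?** Under protocol 12.3.1, no: the period opens at the dose. Under SAP 9.1, yes, if the value was recorded on the first-dose date.

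**Step 2. Does another rule remove it?**

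| Analysis | Rule that would remove a value known to be pre-dose |
|---|---|
| By-visit laboratory and vital-sign summaries | Table 12-1: Day 1 admitted only if post-dose |
| Laboratory and vital-sign thresholds (9.3.2, 9.3.4) | None stated; they use the TE Period, not windows |
| ECG thresholds (9.3.3) | None stated; no Day 1 window in the ECG rows, and all ECG values are used |
| Lowest-SpO2 shift (9.3.5) | None stated; pulse oximetry has no row in Table 12-1 |

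Note 3 does not fill the gap. It settles cases of unknown timing and is silent on a value known to be pre-dose. It is also attached to the window column of Table 12-1, and nothing extends it to the other analyses.

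**Step 3. A constructed example** (not from the documents). A male has a QTcF of 455 ms before the Day 1 dose and 430 ms at Week 48. Table 12-5 classes more than 450 and less than 500 ms in males as borderline. Literal SAP wording gives one TE borderline event; the protocol definition gives none.

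**Step 4. What one extra occasion could do.** Let k be the number of scheduled post-dose occasions in protocol Table 3-1. The lower value leaves out the Safety Follow-up Visit, which may be replaced or fall after the TE Period ends.

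- ECG: k = 1 or 2 (Week 48, Safety Follow-up).
- Coagulation: k = 2 or 3 (Weeks 24 and 48, Safety Follow-up).
- Chemistry, hematology, vital signs, SpO2: k = 4 or 5 (Weeks 12, 24, 36 and 48, Safety Follow-up).

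Assume a chance q of an abnormal value at each occasion, the same at every occasion and independent between occasions. The documents give no such rate. Then P(at least 1 event) = 1 − (1 − q)^k, and including Day 1 replaces k by k + 1:

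| Occasions | q = 1% | q = 5% | q = 10% |
|---|---|---|---|
| 1 | 1.0% | 5.0% | 10.0% |
| 2 | 2.0% | 9.8% | 19.0% |
| 3 | 3.0% | 14.3% | 27.1% |
| 4 | 3.9% | 18.5% | 34.4% |
| 5 | 4.9% | 22.6% | 41.0% |
| 6 | 5.9% | 26.5% | 46.9% |

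The effect is the step from one row to the next, q(1 − q)^k. For ECG with k = 2 it is 0.98 points at q = 1% and 8.10 points at q = 10%, or 1.6 to 13.0 of 160 subjects. For chemistry with k = 5 it is 0.95 to 5.90 points, or 1.5 to 9.4 subjects. One subject is 100/160 = 0.625 points.

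These steps assume that every subject has a pre-dose Day 1 value in the analysis data. They also assume independence; persistent differences between subjects at the same average rate make the step smaller. They show the mechanism and are not an estimate.

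**The case against.** **The SAP's intent is visible.** Appendix A separates pre-dose from post-dose on the first-dose date and, when in doubt, treats a scheduled value as pre-dose. A reader might infer from SAP 9.1 alone that the sponsor has decided to report pre-dose values as treatment-emergent. The documents do not support that. What stands is narrower: the intended handling is not carried into the threshold and shift analyses.

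**Day-level wording is not confined to the SAP.** The protocol's own definition of a treatment-emergent adverse event (12.3.4.1) works from the first-dose date, as does SAP 9.3.1. This stands. It is a reason not to move the whole TE start to the time of dosing, which would conflict with that definition.

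**The maximum/minimum item is not evidence.** It sits in the list on unscheduled visits. It tells the programmer how to use unscheduled values and does not bring scheduled Day 1 values in. This also stands.

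**The reach may be small.** Protocol 9.1.1 expects Day 1 to coincide with the last parent-study visit, and assessments specified at that visit need not be repeated if Day 1 falls within 1 day of it. For those subjects the pre-dose value may exist only as a parent-study record, and the SAP does not say whether such records enter these analyses. This stands and leaves the number affected unknown.

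**The consequence is limited.** There is no testing and no comparison between groups, and an error would over-report events. Subjects treated with ELX/TEZ/IVA in the parent study may already be on the same regimen, so their Day 1 value is not an untreated one. This lowers the importance of the point but does not make the wording right.

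**Conclusion.** Wrong as written; minor. Followed literally, SAP 9.1 lets a pre-dose value recorded on the first-dose date count in the TE threshold analyses and the lowest-SpO2 shift. That departs from protocol 12.3.1, and no rule in the SAP prevents it. ECG thresholds and SpO2 are the most exposed. By-visit laboratory and vital-sign summaries are protected.

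The direction is possible over-counting of events; the size is unknown. A reader might infer from the illustrative table that the percentages will rise by several points. The documents do not support that, because the rates, the independence and a Day 1 record for every subject are all assumptions. It can be said only that the literal wording adds at most one scheduled occasion per subject, and that each subject wrongly counted moves a percentage by 0.625 points at 160 subjects.

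**What to change.** Keep the date-based start for adverse events and medications, and add to SAP 9.1:

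*For laboratory, ECG, vital sign and pulse oximetry data, measurements on the first-dose date that are known to be pre-dose, or are classed as pre-dose under Appendix A note 3, are not in the TE Period; this applies to threshold, shift and maximum/minimum analyses as well as to visit windows.*

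The cost is one sentence in a SAP amendment and one program flag before database lock. No new data are needed. Event counts can only stay the same or fall.

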## 9.2 Background Characteristics

### 9.2.1 Subject Disposition

Subject disposition will be summarized for the All Subjects Set. The number and percentage of subjects in the following categories will be summarized as appropriate:

- All Subjects Set
- Safety Set
- Completed Treatment
- Prematurely discontinued treatment and the reasons for discontinuation
- Completed study
- Prematurely discontinued study and the reasons for discontinuation
- Departed Study VX20-445-121 to participate in another qualified Vertex study
- Departed Study VX20-445-121 to participate in another qualified Vertex study and returned to VX20-445-121

A listing will be provided for subjects who discontinued treatment or who discontinued study with reasons for discontinuation. A separate listing will be provided for subjects who depart from the study.

## **9.2.2 Demographics and Baseline Characteristics**

Demographics and baseline characteristics will be summarized by descriptive summary statistics for the Safety Set. Demographic data will include the following:

- Age at parent study baseline (in years)
- Sex (female and male)
- Ethnicity (Hispanic or Latino, not Hispanic or Latino, and not collected per local regulations)
- Race (White, Black or African American, Asian, American Indian or Alaska Native, Native Hawaiian or Other Pacific Islander, Not Collected per Local Regulations and Other)
- Country

Parent study baseline characteristics will include the following:

- Weight (kg)
- Height (cm)
- BMI (kg/m^2)

Disease characteristics based on parent study baseline will include the following:

- ppFEV1 at parent study baseline (<30, ≥30 to <40, ≥ 40 to <70, ≥70 to ≤90, and >90)
- ppFEV1 at parent study baseline (continuous)
- Prior use of dornase alfa (Yes, No)
- Prior use of azithromycin (Yes, No)
- Prior use of inhaled antibiotic (Yes, No)
- Prior use of any bronchodilator (Yes, No)
- Prior use of any inhaled bronchodilator (Yes, No)
- Prior use of any inhaled hypertonic saline (Yes, No)
- Prior use of any inhaled corticosteroids (Yes, No)

Prior medication use definition is same as that for the baseline characteristics summary presented in the parent studies.

## **9.2.3 Medical History**

Medical history (referenced to the start of parent study) will be coded by using the Medical Dictionary for Regulatory Activities (MedDRA). Medical history will be summarized descriptively by System Organ Class (SOC) and Preferred Term (PT) based on the Safety Set. The corresponding data listing will also be provided.

## **9.2.4 Prior and Concomitant Medications**

Medications will be coded using the World Health Organization-Drug Dictionary and categorized as follows:

- **Prior medication:** any medication that was administered within the 56 days before the first dose of study drug in this open-label study. For subjects who were enrolled in another qualified Vertex study before completing this study and resume participation in this study, any new or changed medication administered after the Departing Visit and prior to the first dose of this study's drug after resuming participation will also be considered as prior medication.
- **Concomitant medication:** medication continued or newly received during the TE Period in this open-label study.
- **Post-treatment medication:** medication continued or newly received after the TE Period in this open-label study.

A given medication may be classified as a prior medication, a concomitant medication, or a post-treatment medication; both prior and concomitant; both concomitant and post-treatment; or prior, concomitant, and post-treatment.

If a medication has a missing or partially missing start/end date or time and if it cannot be determined whether it was taken before initial dosing, concomitantly during the TE Period, or beyond the TE Period, it will be considered in all 3 categories of prior, concomitant, and post-treatment medication. Details for imputing missing or partial start and/or stop dates of medication are described in [Appendix B](#).

Prior medications and concomitant medications will be summarized descriptively by Preferred Name based on the Safety Set by 1) preferred name (PN); and 2) anatomic class (ATC) level 1, ATC level 2, and PN. Post-treatment medications will be provided separately in an individual subject data listing.

